4 STUDY DESIGN

4.1 Overall Design

Approximately 2,400 healthy infants will be randomly assigned to receive V114 (n \approx 2,000) or Prevnar 13™ (n \approx 400) at Visits 1, 2, 3, and 5 (approximately 2, 4, 6, and 12 to 15 months of age, respectively) in the following ratios based on gestational age:

- Full-term infants (gestational age ≥ 37 weeks) 5:1 to V114 or Prevnar 13™
- Premature infants (gestational age < 37 weeks) 1:1 to V114 or Prevnar 13™

It is estimated that approximately 1 to 2% of the overall study population will have a gestational age <37 weeks and will be eligible for inclusion in the Premature Infant Immunogenicity Substudy. There is no prespecified number of premature infants targeted for enrollment in the substudy.

Participants will be followed for local and systemic AEs through Day 14 following each vaccination with V114 or Prevnar 13™. Information for SAEs and deaths, regardless of whether the events are considered to be vaccine-related by the investigator, will be collected from the time consent is signed through completion of participation in the study. An external Data Monitoring Committee (DMC) will conduct a periodic review of safety and tolerability data for the V114 Phase 3 pediatric program. A description of the structure, function, and guidelines for decision making by the DMC, along with the timing and content of the safety reviews will be outlined in the DMC charter. Information regarding the composition of the DMC is provided in Appendix 1.

In addition to the safety assessments, participants in the Premature Infant Immunogenicity Substudy, will also have blood samples for immunogenicity assays drawn at 3 timepoints: (1) 30 days Postdose 3 (PD3), (2) immediately prior to Dose 4, and (3) 30 days Postdose 4 (PD4).

After completion of immunogenicity testing, serum samples will be stored to conduct any additional study-related testing as required by regulatory agencies or the Sponsor. For randomized study participants who provided consent for future biomedical research, leftover sera from the study may be used for the development and/or validation of pneumococcal assays after completion of all study-related immunogenicity testing.

Specific procedures to be performed during the study, as well as their prescribed times and associated visit windows, are outlined in the SoA in Section 1.3. Details of each procedure are provided in Section 8.

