6.3 Measures to Minimize Bias: Randomization and Blinding

6.3.1 Intervention Assignment

Intervention allocation/randomization will occur centrally using an interactive response technology (IRT) system. There are 2 study intervention arms. Full-term infant participants (gestational age ≥ 37 weeks) will be assigned randomly in a 5:1 ratio to receive V114 or Prevnar 13™. Premature infant participants (gestational age < 37 weeks) in the immunogenicity substudy will be assigned randomly in a 1:1 ratio to receive V114 or Prevnar 13™.

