Membership in Tier 2 requires that at least 1% of the participants in either treatment group exhibit the event. The threshold of at least 1% was chosen because when less than 1% of participants report AEs in both groups with more events in the V114 group, the 95% CI for the between-group difference in percent incidence will always include zero. Note that when less than 1% of participants report AEs in both groups but with more events in the Prevnar 13™ group or equal in both groups, the 95% CI for the between-group difference may exclude zero. However, the clinical significance of these differences is unknown given the small number of participants who report AEs in this situation (fewer than 4 subjects in each group) and; therefore, these AEs will be categorized as Tier 3 events. Because many 95% CIs for Tier 2 events may be provided without adjustment for multiplicity, the CIs should be regarded as a helpful descriptive measure to be used in review, not a formal method for assessing the statistical significance of the between-group differences in AEs and safety parameters that meet predefined limits of change.

In addition to individual events that occur in at least 1% of participants in any treatment group, the broad AE categories consisting of the proportion of participants with any AE, a vaccine-related AE, an SAE, a vaccine-related SAE, discontinuation due to an AE, and the proportion of participants who died will be considered Tier 2 endpoints.

Tier 3 Events

Safety endpoints that are not Tier 1 or 2 events are considered Tier 3 events. Only point estimates by treatment group are provided for Tier 3 safety parameters.

Table 4 Analysis Strategy for Safety Parameters

Safety Tier	Safety Endpoint [†]	p-Value	95% CI for Between-Group Comparison	Descriptive Statistics
Tier 1	Injection-site redness/erythema (Days 1 to 14)	X	X	X
	Injection-site swelling (Days 1 to 14)	X	X	X
	Injection-site tenderness/pain (Days 1 to 14)	X	X	X
	Injection-site hard lump/induration (Days 1 to 14)	X	X	X
	Irritability (Days 1 to 14)	X	X	X
	Drowsiness/somnolence (Days 1 to 14)	X	X	X
	Hives or welts/urticaria (Days 1 to 14)	X	X	X
	Appetite loss/decreased appetite (Days 1 to 14)	X	X	X
Tier 2	Any AE [†]		X	X
	Any Vaccine-Related AE [†]		X	X
	Any SAE [†]		X	X
	Any Vaccine-Related SAE [†]		X	X
	Discontinuation due to AE [†]		X	X
	Death [†]		X	X
	Maximum temperature measurements meeting the Brighton Collaboration cut points (Days 1 to 7)		X	X

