Tier 3	Specific AEs by SOC and PT [‡] (incidence ≥4 of participants in one of the vaccination groups)		X	X
	Specific AEs by SOC and PT [‡] (incidence <4 of participants in all of the vaccination groups)			X

[†] These endpoints are broad adverse event categories. For example, descriptive statistics for the safety endpoint of “Any AE” will provide the number and percentage of participants with at least one AE.
[‡] Includes only those endpoints not pre-specified as Tier 1 or not already pre-specified as Tier 2 endpoints.
 AE = adverse event; CI = confidence interval; PT = preferred term; SAE = serious adverse event; SOC = system organ class; X = results will be provided

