Membership in Tier 2 requires that at least 1% of the participants in either treatment group exhibit the event. The threshold of at least 1% was chosen because when less than 1% of participants report AEs in both groups with more events in the V114 group, the 95% CI for the between-group difference in percent incidence will always include zero. Note that when less than 1% of participants report AEs in both groups but with more events in the Prevnar 13™ group or equal in both groups, the 95% CI for the between-group difference may exclude zero. However, the clinical significance of these differences is unknown given the small number of participants who report AEs in this situation (1% of the participants in either treatment group) and; therefore, these AEs will be categorized as Tier 3 events. Because many 95% CIs for Tier 2 events may be provided without adjustment for multiplicity, the CIs should be regarded as a helpful descriptive measure to be used in review, not a formal method for assessing the statistical significance of the between-group differences in AEs and safety parameters that meet predefined limits of change.

In addition to individual events that occur in at least 1% of participants in any treatment group, the broad AE categories consisting of the proportion of participants with any AE, a vaccine-related AE, an SAE, a vaccine-related SAE, discontinuation due to an AE, and the proportion of participants who died will be considered Tier 2 endpoints.

Tier 3 Events

Safety endpoints that are not Tier 1 or 2 events are considered Tier 3 events. Only point estimates by treatment group are provided for Tier 3 safety parameters.

Table 3 Analysis Strategy for Safety Parameters

Safety Tier	Safety Endpoint [†]	p-Value	95% CI for Between-Group Comparison	Descriptive Statistics
Tier 1	Injection-site redness/erythema (Days 1 to 14)	X	X	X
	Injection-site swelling (Days 1 to 14)	X	X	X
	Injection-site tenderness/pain (Days 1 to 14)	X	X	X
	Injection-site hard lump/induration (Days 1 to 14)	X	X	X
	Irritability (Days 1 to 14)	X	X	X
	Drowsiness/somnolence (Days 1 to 14)	X	X	X
	Hives or welts/urticaria (Days 1 to 14)	X	X	X
	Appetite loss/decreased appetite (Days 1 to 14)	X	X	X
Tier 2	Any AE [†]		X	X
	Any Vaccine-Related AE [†]		X	X
	Any SAE [†]		X	X
	Any Vaccine-Related SAE [†]		X	X
	Discontinuation due to AE [†]		X	X
	Death [†]		X	X
	Maximum temperature measurements meeting the Brighton Collaboration cut points (Days 1 to 7)		X	X

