Tier 3	Specific AEs by SOC and PT [‡] (incidence $\geq 1\%$ of participants in one of the vaccination groups)		X	X
	Specific AEs by SOC and PT [‡] (incidence $< 1\%$ of participants in all of the vaccination groups)			X

[†] These endpoints are broad adverse event categories. For example, descriptive statistics for the safety endpoint of “Any AE” will provide the number and percentage of participants with at least one AE.
[‡] Includes only those endpoints not pre-specified as Tier 1 or not already pre-specified as Tier 2 endpoints.
 AE = adverse event; CI = confidence interval; PT = preferred term; SAE = serious adverse event;
 SOC = system organ class; X = results will be provided

Laboratory AEs will not be reported in summary tables as laboratory testing is not performed as part of the study and thus such AEs would only be reported spontaneously. A listing of laboratory AEs will be provided.

A supportive analysis comparing the proportion of participants reporting each of the solicited complaints on the VRC will be conducted in support of the primary safety analyses that are based on solicited AEs. This supportive analysis will use the methodology specified in Table 3 for solicited AEs. The analysis will be conducted on the subset of the APaT population who entered solicited complaints data on the VRC.

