3.9.2 Sample Size and Power for Safety Analyses

The probability of observing at least one SAE in this study depends on the number of participants vaccinated and the underlying incidence of participants with an SAE in the study population. Calculations below assume that 100% of the randomized participants will be evaluable for safety analyses. There is an 80% chance of observing at least one SAE among 2,000 participants in V114 group if the underlying incidence of an SAE is 0.08% (1 of every 1243 participants receiving the vaccine). There is a 50% chance of observing at least one SAE among 2,000 participants in V114 group if the underlying incidence of an SAE is 0.03% (1 of every 2,886 participants receiving the vaccine). If no SAEs are observed among 2,000 participants, this study will provide 97.5% confidence that the underlying percentage of participants with an SAE is <0.18% (one in every 543 participants).

Table 5 summarizes the percentage point differences between the 2 vaccination groups that could be detected with 80% probability for a variety of hypothetical underlying incidences of an AE. These calculations assume 2,000 participants in V114 group and 400 participants in Prevnar 13™ group, and are based on a 2-sided 5% alpha level. The calculations are based on an asymptotic method proposed by Farrington and Manning (1990) [Ref. 5.4: 04FS6L]; no multiplicity adjustments were made.

Table 5 Differences in Incidence of Adverse Event Rates Between the 2 Vaccination Groups That Can be Detected With an ~80% Probability (Assuming 2-sided 5% Alpha Level with 2000 Participants in V114 Group and 400 Participants in Prevnar 13™ Group)

Incidence of Adverse Event		Risk Difference
V114 (%)	Prevnar 13™ (%)	Percentage Points
1.6	0.1	1.5
4.9	2	2.9
9.0	5	4.0
15.2	10	5.2
21.0	15	6.0
26.6	20	6.6
37.3	30	7.3

Incidences presented here are hypothetical and do not represent actual adverse experiences in either group. Based on an asymptotic method proposed by Farrington and Manning (1990) [Ref. 5.4: 04FS6L]

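### Does the reason given for the 1% Tier 2 cut-off fail at the group sizes the randomisation will produce?

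*Combined protocol and SAP*

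**What the plan says.** Section 3.6.2 of the supplemental SAP (sSAP) and section 9.6.2 of the protocol sort adverse events into three tiers. A specific event joins Tier 2, and gets a Miettinen and Nurminen (M&N) 95% interval for the between-group difference, if at least 1% of either group reports it. Below that it is Tier 3, with point estimates by group only.

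Both documents justify the threshold in the same words: when fewer than 1% in both groups report the event, "with more events in the V114 group, the 95% CI for the between-group difference in percent incidence will always include zero". The next sentence concedes that with more events on Prevnar 13, "or equal in both groups, the 95% CI for the between-group difference may exclude zero". It accepts Tier 3 for those events because the numbers are small. The protocol describes the numbers as "fewer than 4 subjects in each group"; the sSAP puts 1% in that place. Protocol Table 4 states its cut-off as "incidence ≥4 of participants in one of the vaccination groups", whereas sSAP Table 3 uses 1%.

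On group sizes, sSAP section 3.9.2 says: "These calculations assume 2,000 participants in V114 group and 400 participants in Prevnar 13™ group". Full-term infants are randomised 5:1, but under protocol section 6.3.1 premature infants "in the immunogenicity substudy will be assigned randomly in a 1:1 ratio to receive V114 or Prevnar 13™". Protocol section 4.1 adds: "It is estimated that approximately 1 to 2% of the overall study population will have a gestational age <37 weeks".

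**The concern.** The justification is a universal statement, so one counterexample within the design refutes it. It appears to have been checked at exactly 2,000/400, where it holds by a very small margin. Any premature infants randomised 1:1 move participants from V114 to Prevnar 13, and that margin could disappear.

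Safety is the primary objective, and the cut-off decides which specific terms get an interval. If the reason given for it is wrong, an excess on V114 whose interval excludes zero could be shown without that interval, while the plan tells the reader this cannot happen.

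The text around it is also loose. Equal rates cannot give an interval that excludes zero, so the remark about equality must refer to counts. The protocol's limit of 4 participants equals 1% only when the Prevnar 13 group has exactly 400.

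**Working it through.** **Group sizes.** With 2,400 infants of whom P are premature, the expected Prevnar 13 group is P/2 + (2,400 − P)/6 = 400 + P/3.
- 1% premature: P = 24, giving 1,992/408.
- 2% premature: P = 48, giving 1,984/416.

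**Test at a difference of zero.** When Prevnar 13 has no events and V114 has x, the restricted estimate at zero difference is the pooled rate x/N. The M&N statistic, with its N/(N − 1) variance factor, then reduces to

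χ² = (N − 1) · x · n₂ / [(N − x) · n₁],

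where n₁ is V114 and n₂ is Prevnar 13. The 95% interval excludes zero when χ² exceeds 3.8415 (z above 1.960).

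**The plan's statement at 2,000/400.** The largest V114 count below 1% is 19. Then χ² = 2,399 × 19 × 400 / (2,381 × 2,000) = 3.829, z = 1.957, and the interval is −0.003 to 1.479 percentage points. Zero is included. A scan of every table below 1% in both groups with more V114 events finds no exception, so the statement is correct at these sizes.

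**19 against 0 at the expected sizes.**

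| V114 / Prevnar 13 | V114 rate | χ² | z | 95% interval (percentage points) |
|---|---|---|---|---|
| 1,992/408 | 0.954% | 2,399 × 19 × 408 / (2,381 × 1,992) = 3.921 | 1.980 | 0.019 to 1.485 |
| 1,984/416 | 0.958% | 2,399 × 19 × 416 / (2,381 × 1,984) = 4.014 | 2.003 | 0.041 to 1.491 |

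Both intervals exclude zero. With 18 against 0 at 1,984/416, z = 1.950 and zero is included. The scan shows 19 against 0 to be the only failing table with the higher rate on V114.

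**Where it breaks.** At 1,999/401, χ² = 3.840 and the statement holds. At 1,998/402 (6 premature infants), χ² = 3.852 and it fails. The result is not peculiar to a total of 2,400. At totals checked from 2,300 to 2,450 with 1% or 2% premature, the largest V114 count below 1% (19 or 20) against none excludes zero each time.

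**Reading by count.** At 2,000/400, 3 against 3 gives z = −2.19, which confirms that the remark about equality refers to counts. On that reading 5 against 4 also breaks the statement at the expected sizes (z = −2.20 at 1,992/408 and −2.15 at 1,984/416), because 4/408 = 0.98% and 4/416 = 0.96% are below 1%. But V114 then has the lower rate (5/1,992 = 0.25%), so no V114 excess is involved.

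**Dependence on stratification.** The documents specify no stratified M&N analysis. If one were used with Mantel-Haenszel-type weights (an assumption), 19 against 0 with every event in a full-term infant gives z = 1.957, and zero is included. With 18 full-term and 1 premature, z = 2.117, and it is excluded.

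**How likely.** If both groups share a true rate r, the probability of exactly 19 against 0 is the product of the two binomial probabilities. At 1,992/408 it is 0.0005 at r = 0.5% and peaks at 0.0026 near r = 0.79%. At 1,984/416 the peak is 0.0024.

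**The case for a change.** The strongest case for a change is that the sentence is an assurance in a safety trial and is false under the design's own allocation. The plan expects 24 to 48 premature infants, and about 6 are enough to break it. The sSAP also revised the neighbouring wording and carried this sentence over unchanged. All of that stands for the unstratified analysis, the only one the documents describe.

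What does not follow is a need to act. Three remedies suggest themselves.

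- **Soften or qualify the sentence.** This is more accurate, but it leaves the cut-off, every interval and every conclusion as they are.
- **Add an interval for any event below 1% whose interval excludes zero on the V114 side.** Whether an interval appears would then depend on its result and on one direction, which is poor practice for unadjusted descriptive intervals.
- **Return to a cut-off of 4 participants.** No excluded table with more V114 events would then exclude zero at these sizes. But V114 terms at 4/2,000 = 0.2% would qualify, adding many unadjusted intervals to cover one table and undoing the 1% that the sSAP uses in both text and table.

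The mismatch with protocol Table 4 is real, but the sSAP's consistent 1% settles which rule the analysts will apply.

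**Conclusion.** The word 'always' overstates the case, but the 1% cut-off can stand and no change is needed. The exception is a single table, 19 against 0, whose lower limit moves from −0.003 at 2,000/400 to between 0.019 and 0.041 percentage points at the expected split. A reader would judge the event the same way in either case.

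Little would be hidden if that table occurred. Tier 3 still reports about 0.95% against 0%. Solicited events are Tier 1 and get intervals and p-values. Any serious event, death and discontinuation due to an adverse event get an interval at any frequency. The plan tests no formal hypothesis and calls these intervals descriptive, so no decision depends on which side of zero one of them falls.

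This rests on an unstratified M&N interval, about 2,400 infants analysed with 1% to 2% premature, and the sSAP's 1% taking precedence over the protocol's 4 participants. The probability of at most about 0.26% per term assumes equal true rates. A true V114 excess would make the table more likely, but it would still appear in the point estimates.

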3. ANALYTICAL AND METHODOLOGICAL DETAILS

3.1 Statistical Analysis Plan Summary

Key elements of the statistical analysis plan are summarized below; the comprehensive plan is provided in Sections 3.2 through 3.12.

Study Design Overview	A Phase 3, Multicenter, Randomized, Double-blind, Active Comparator-controlled Study to Evaluate the Safety and Tolerability of V114 in Healthy Infants (PNEU-LINK)
Intervention Assignment	Approximately 2400 healthy infants approximately 2 months of age will be enrolled. 
 • Full-term infants (gestational age ≥ 37 weeks) will be randomly assigned in a 5:1 ratio to a complete dosing schedule of V114 or Prevnar 13™. • Premature infants (gestational age < 37 weeks) will be randomly assigned in a 1:1 ratio to a complete dosing schedule of V114 or Prevnar 13™
Analysis Populations	Safety: All Participants as Treated (APaT) Immunogenicity: Per-Protocol (PP) and Full Analysis Set (FAS) population for the Premature Infant Immunogenicity Substudy
Primary Endpoint(s)	
 • Proportion of participants with solicited injection-site AEs (swelling, redness/erythema, tenderness/pain, and hard lump/induration) from Day 1 through Day 14 following any vaccination with V114 or Prevnar 13™ • Proportion of participants with solicited systemic AEs (irritability, drowsiness/somnolence, appetite lost/decreased appetite, and hives or welts/urticaria) from Day 1 through Day 14 following any vaccination with V114 or Prevnar 13™ • Proportion of participants with vaccine-related SAEs from Day 1 through completion of study participation
Key Secondary Endpoint(s)	Premature Infant Immunogenicity Substudy only: 
 • Anti-pneumococcal polysaccharide (PnPs) serotype-specific Immunoglobulin G (IgG) Geometric Mean Concentrations (GMCs) for the 15 serotypes contained in V114 at 30 days PD3, prior to Dose 4 and at 30 days PD4 • Anti-PnPs serotype-specific IgG response rates (proportion of participants meeting serotype-specific IgG threshold value of ≥ 0.35 $\mu\text{g/mL}$) for the 15 serotypes contained in V114 at 30 days PD3
Statistical Methods for Key Immunogenicity Analyses	Immunogenicity analyses will be conducted for each of the 15 pneumococcal serotypes contained in V114 separately. To address the immunogenicity objectives, evaluation of the anti-PnPs serotype-specific IgG GMCs and response rates will be summarized descriptively.

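### Rare Tier 2 categories, including the primary endpoint of vaccine-related SAE, keep an asymptotic interval that can exclude zero in V114's favour on one Prevnar 13 event

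*Combined protocol and SAP*

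**What the plan says.** Supplemental SAP 3.1 lists as a primary endpoint: "Proportion of participants with vaccine-related SAEs from Day 1 through completion of study participation".

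Supplemental SAP 3.6.2 sorts safety endpoints into tiers. Tier 2 endpoints get a point estimate and a Miettinen-Nurminen (M&N) 95% interval for the between-group difference, with no p-value. An individual adverse event enters Tier 2 only if at least 1% of either group has it. The plan explains the threshold. Below 1% in both groups with more events on V114, the interval always includes zero. With more events on Prevnar 13, or equal numbers, "the 95% CI for the between-group difference may exclude zero". The plan says the clinical meaning of such a result is unknown with so few events, and sends these events to Tier 3, where no interval is given.

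The next paragraph places the broad categories in Tier 2 as well: any AE, vaccine-related AE, SAE, "a vaccine-related SAE, discontinuation due to an AE, and the proportion of participants who died will be considered Tier 2 endpoints". No incidence condition is attached, and Table 3 marks a between-group interval for each. Protocol 9.6.2 and its Table 4 treat these categories in the same way.

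**The concern.** The plan recognises that the M&N interval misbehaves with sparse events and roughly 5:1 arms, and withdraws it for individual adverse events. It keeps the interval for vaccine-related SAE, death and discontinuation due to an AE, where counts are likely to be very small.

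At stake is how the most serious outcomes of a safety trial are presented. One chance event on Prevnar 13 would put a 95% interval lying wholly on V114's side of zero into the report for death or for a primary endpoint. A reader could take that as a safety advantage when the data show almost nothing.

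**Working it through.** **Inputs**
- Group sizes, supplemental SAP 3.9.2: "These calculations assume 2,000 participants in V114 group and 400 participants in Prevnar 13™ group".
- Allocation, supplemental SAP 3.1: full-term infants "will be randomly assigned in a 5:1 ratio to a complete dosing schedule of V114 or Prevnar 13™"; premature infants "will be randomly assigned in a 1:1 ratio to a complete dosing schedule of V114 or Prevnar 13™".
- Premature share, protocol 4.1: "approximately 1 to 2% of the overall study population will have a gestational age <37 weeks".
- Level: 95% two-sided, critical value 1.96.
- The event splits are scenarios, not document figures. They are written V114 v Prevnar 13.

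**Method.** For a hypothesised difference δ, with rates p̃ fitted under that difference and N = n_V + n_P:

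z(δ) = (x_V/n_V − x_P/n_P − δ) / √{[p̃_V(1−p̃_V)/n_V + p̃_P(1−p̃_P)/n_P] × N/(N−1)}

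The limits are the values of δ where |z| = 1.96. Zero is excluded when |z(0)| > 1.96.

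**Step 1: reproduce the plan's rationale.** Below 1% means at most 19/2000 and 3/400. Over all such splits, none with more events on V114 excludes zero; 19 v 0 gives -0.003 to 1.48 points. The splits that exclude zero are 0 v 1, 0 v 2, 0 v 3, 1 v 2, 1 v 3, 2 v 3 and 3 v 3, all in V114's favour. The plan's statement is correct.

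**Step 2: one event.** For 0 v 1 the pooled rate is 1/N, so p(1−p) = (N−1)/N². The variance is (N−1)/N² × N/(n_V n_P) × N/(N−1) = 1/(n_V n_P). The difference is −1/n_P. Hence z² = n_V/n_P = 2000/400 = 5, above 1.96² = 3.84. The result follows from the allocation ratio alone.

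| Split (2000 v 400) | M&N 95% interval, points | Fisher p |
|---|---|---|
| 0 v 1 | -1.40 to -0.04 | 0.167 |
| 1 v 2 | -1.76 to -0.05 | 0.074 |
| 3 v 3 | -2.04 to -0.05 | 0.062 |

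For 0 v 1, Fisher p = 400/2400 = 1/6.

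**Step 3: effect of the premature infants.** With premature share s, n_P = 2400 × [(1−s)/6 + s/2]. This is 408 at 1% and 416 at 2%. The 0 v 1 interval becomes -1.38 to -0.04 (1992/408) and -1.35 to -0.04 (1984/416). The ratio falls below 3.84 only when s exceeds about 12%.

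**Step 4: how often this happens with equal true risk.** Binomial probabilities were summed over all splits with z(0) < −1.96.

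| True risk in both arms | Zero excluded in V114's favour |
|---|---|
| 0.01% | 3.2% |
| 1 in 2,886 | 6.8% |
| 0.05% | 7.3% |
| 1 in 1,243 | 7.0% |
| 0.1% | 6.5% |
| 0.2% | 4.4% |

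The nominal rate is 2.5% per side. The rates 1 in 2,886 and 1 in 1,243 are the plan's own SAE illustrations in 3.9.2. Exclusion in the other direction is essentially nil at these risks, so total two-sided error is the same 3.2% to 7.3%, against 5%. At 0.05% the single split 0 v 1 contributes 0.9995^2399 × 400 × 0.0005 = 6.0%.

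**Step 5: an exact replacement.** Order the outcomes by z(0) and maximise the tail probability over the common rate. Zero stays inside the 95% interval if the one-sided p exceeds 0.025.

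| Split | One-sided exact p | Zero included? |
|---|---|---|
| 0 v 1 | 0.074 | yes |
| 1 v 2 | 0.031 | yes |
| 3 v 3 | 0.074 | yes |
| 0 v 2 | 0.009 | no |
| 1 v 3 | 0.011 | no |
| 2 v 3 | 0.016 | no |

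**The case against.** The strongest reply is that nothing is decided on these intervals. The study has no formal hypothesis, and Tier 2 carries no p-value. Supplemental SAP 3.6.2 calls the intervals descriptive and rests the assessment on clinical review. The counts 0 and 1 would stand beside the interval. The Malaysia appendix (protocol 10.7.1) applies the same methods to a tolerability hypothesis but sets no criterion that turns on an interval excluding zero. This stands, and it limits the severity. It does not make the interval right: the plan did not regard the descriptive label as enough for individual events below 1%, and withdrew their intervals.

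A second reply is that an exact interval only moves the problem, since 0 v 2, 1 v 3 and 2 v 3 still exclude zero. That is true, but those exclusions fall within a controlled one-sided error of 2.5%. The exclusions at 0 v 1, 1 v 2 and 3 v 3 do not.

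Two stronger readings are tempting. A reader might infer that M&N hides V114 harm, because 19 v 0 still includes zero. The cause is the 400 controls: with 20 events in total and equal risk, all fall on V114 with probability about (5/6)^20 = 0.026, so even that split is only borderline evidence. A reader might also call the interval invalid. Total two-sided error is below 5% at 0.01% and at 0.2%, and reaches only 7.3% in between. The fault is moderate inflation, all of it in one tail.

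**Conclusion.** The concern holds for vaccine-related SAE, death and discontinuation due to an AE. The plan applies to them, at any incidence, an interval that it withdraws for individual events in the same situation. At the planned sizes a single Prevnar 13 event produces an interval excluding zero in V114's favour. If true risks are equal and lie between 0.01% and 0.2%, this kind of error occurs in about 3.2% to 7.3% of trials instead of 2.5%.

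This assumes about 2,000 and 400 infants analysed, an unstratified M&N interval, and true risks low enough that only a few events occur. The documents give no expected rate for these three categories. No calculation was made for a stratified interval, so nothing is claimed about one.

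It should be fixed, but it does not threaten the trial's conclusions. The documents do not support reading it as a route to a formal claim that V114 is safer, because no such test or decision rule exists.

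**What to change.** In supplemental SAP 3.6.2 and Table 3, and in protocol 9.6.2 and Table 4, add a rule for vaccine-related SAE, death and discontinuation due to an AE. When fewer than 1% of participants in both groups have the event, do one of the following, chosen before unblinding:

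- replace the M&N interval with an exact unconditional 95% interval for the difference, based on the score statistic; or
- give counts and percentages with within-group Clopper-Pearson intervals, and no between-group interval. For 0/2000 the upper limit is 1 − 0.025^(1/2000) = 0.18%, which is the plan's own zero-event figure in 3.9.2.

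Keep M&N at 1% and above.

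The cost is a few lines of text, a standard routine, somewhat wider intervals and a prespecified change of method at 1%. The exact interval removes the false V114 benefit at 0 v 1, 1 v 2 and 3 v 3; the second option removes the between-group interval altogether. Neither improves the ability to detect V114 harm, which the 400 controls limit.
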